6.6.5. Time to treatment discontinuation or failure due to toxicity

Time to treatment discontinuation or failure due to toxicity (here onwards referred to as time to treatment failure (TTF), for simplicity) is defined as the time from first dose of study treatment to discontinuation of study treatment (discontinuation of either avelumab or axitinib for arm A) due to an adverse event or death due to study treatment toxicity.

TTF (in months) = [Date of study treatment discontinuation – start date of study treatment +1]/30.4375

TTF will be summarized using simple descriptive statistics (mean, SD, median, min, max, Q1, Q3).

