### **Time to treatment discontinuation/failure due to toxicity**

Time to treatment discontinuation/failure due to toxicity is defined as the time from first dose of study treatment to discontinuation of study treatment due to an adverse event or death due to study treatment toxicity. Time to treatment discontinuation/failure due to toxicity will be summarized by treatment arm using Kaplan-Meier methodology and displayed graphically, where appropriate. The median time to treatment discontinuation/failure due to toxicity and 95% CI for the median will be provided for each treatment arm.

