2.1. Study Objectives

Primary Objective

- To demonstrate that avelumab in combination with axitinib is superior to sunitinib monotherapy in prolonging PFS or OS in the first-line treatment of PD-L1 positive patients with advanced renal cell carcinoma (aRCC).

Secondary Objectives

- To demonstrate that avelumab in combination with axitinib is superior to sunitinib monotherapy in prolonging PFS in the first-line treatment of patients with aRCC unselected for PD-L1 expression;
- To demonstrate that avelumab in combination with axitinib is superior to sunitinib monotherapy in prolonging OS in the first-line treatment of patients with aRCC unselected for PD-L1 expression;
- To evaluate other measures of efficacy of avelumab in combination with axitinib and sunitinib monotherapy in the first-line treatment of aRCC patients;
- To evaluate progression-free survival on next-line of therapy (PFS2);
- To evaluate the overall safety profile of avelumab in combination with axitinib and sunitinib monotherapy in the first-line treatment of aRCC patients;

- To evaluate the population pharmacokinetics of avelumab and axitinib when administered in combination;
- To evaluate the time to treatment discontinuation/failure due to toxicity;
- To evaluate the proportion of patients who discontinued treatment due to toxicity;
- To evaluate candidate predictive biomarkers in pre-treatment tumor tissue that may aid in the identification of a patient subpopulation most likely to benefit from treatment with avelumab in combination with axitinib and sunitinib monotherapy;
- To assess the immunogenicity of avelumab when combined with axitinib;
- To evaluate the effects of avelumab in combination with axitinib and sunitinib monotherapy on patient-reported outcomes.

CCI

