3.2. Secondary Endpoints

3.2.1. Safety endpoints

- Adverse Events (AEs) as graded by National Cancer Institute (NCI) Common Terminology Criteria for Adverse Events (CTCAE) v4.03;

AEs will be graded by the investigator according to the CTCAE v4.03 and coded using the Medical Dictionary for Regulatory Activities (MedDRA);

- Laboratory abnormalities as graded by NCI CTCAE v4.03;
- Vital signs (blood pressure, pulse rate);
- Time to treatment discontinuation/failure due to toxicity;

Time to treatment discontinuation/failure due to toxicity is defined as the time from first dose of study treatment to discontinuation of study treatment (discontinuation of either avelumab or axitinib for arm A) due to an adverse event or death due to study treatment toxicity.

- Treatment discontinuation due to toxicity.

Treatment discontinuation due to toxicity is defined as the discontinuation of study treatment (discontinuation of either avelumab or axitinib for arm A) due to an adverse event or death due to study treatment toxicity.

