6.2.2.7. Duration of response

Duration of Response (DR) is defined, for patients with OR, as the time from the first documentation of objective response (CR or PR) to the date of first documentation of PD or death due to any cause. If a patient has not had an event (PD or death), DR is censored at the date of last adequate tumor assessment. The censoring rules for DR are as described for PFS in Table 9.

$$\text{DR (months)} = [\text{date of event or censoring} - \text{first date of OR} + 1] / 30.4375$$

Kaplan-Meier estimates (product-limit estimates) will be presented by treatment arm together with a summary of associated statistics including the median DR time with 2-sided 95% CIs. In particular, the DR rate at 3, 6, 9, 12, 18, 24, 30 months will be estimated with corresponding 2-sided 95% CIs. The CIs for the median will be calculated according to [Brookmeyer and Crowley](#) and the CIs for the survival function estimates at the time points defined above will be derived using the log-log transformation according to [Kalbfleisch and Prentice](#) (confype=loglog default option in SAS Proc LIFETEST) with back transformation to a CI on the untransformed scale. The estimate of the standard error will be computed using Greenwood's formula.

DR will be displayed graphically and analyzed using Kaplan-Meier methodology. If the number of patients with OR is small, the Kaplan-Meier method may not provide reliable estimates. In this case, only descriptive statistics or listings will be provided.

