6.2.2.8. Time to response

Time to response (TTR) is defined, for patients with OR, as the time from the date of randomization to the first documentation of objective response (CR or PR) which is subsequently confirmed.

$$\text{TTR (in months)} = [\text{first date of OR} - \text{date of randomization} + 1] / 30.4375$$

TTR will be summarized using simple descriptive statistics (mean, SD, median, min, max, Q1, Q3).

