6.2.6.1. Time to and Duration of ADA and nAb response

The ADA and nAb analyses described below will include patients with treatment-induced ADA or nAb, respectively.

Time (weeks) to ADA response is defined as:

$$(\text{Date of first positive ADA result} - \text{date of first dose of avelumab} + 1)/7.$$

Time to ADA response will be summarized using simple descriptive statistics (mean, SD, median, min, max, Q1, Q3).

Duration (weeks) of ADA response is defined as:

$$(\text{Date of last positive ADA result} - \text{date of first positive ADA result} + 1)/7.$$

Duration of ADA response will be censored if:

- the last ADA assessment is positive AND patient is ongoing treatment with avelumab, or

- the last ADA assessment is positive AND patient discontinued treatment with avelumab AND the last planned ADA assessment (30 days after the last dose of avelumab) is after the cut-off date.

Time to nAb response and duration of nAb response are defined similarly based on first and last positive nAb result.

Kaplan-Meier estimates (product-limit estimates) will be presented together with a summary of associated statistics including the median ADA response time with 2-sided 95% CIs. ADA response rates at different timepoints will be estimated with corresponding 2-sided 95% CIs. The CIs for the median will be calculated according to Brookmeyer and Crowley (1982) and the CIs for the survival function estimates will be derived using the log-log transformation according to Kalbfleisch and Prentice (2011) (confotype=loglog default option in SAS Proc LIFETEST) with back transformation to a CI on the untransformed scale. The estimate of the standard error will be computed using Greenwood's formula.

Duration of ADA response will be displayed graphically and analyzed using Kaplan-Meier methodology. If the number of patients with ADA response is small, the Kaplan-Meier method may not provide reliable estimates. In this case, only descriptive statistics or listings will be provided

As data permit, the analyses described above will be repeated for patients with treatment-induced nAb.

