6.6.6. Treatment discontinuation due to toxicity

Treatment discontinuation due to toxicity is defined as the discontinuation of study treatment (discontinuation of either avelumab or axitinib for arm A) due to an adverse event or death due to study treatment toxicity. The number and percentage of patients who discontinue treatment due to toxicity in each treatment arm will be estimated by dividing the number of patients who meet the above criteria by the number of patients in the safety set.

The corresponding exact 2-sided 95% CIs will be provided for each treatment arm, using the Clopper-Pearson method (exact CI for a binomial proportion as computed by default by the FREQ procedure using the EXACT option).

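### SAP 6.6.5 summarises time to toxicity discontinuation with a mean, SD and quartiles and no censoring, where protocol 9.5 specifies Kaplan-Meier, so the result depends on other-cause stopping and on the cut-off date

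*SAP*

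**What the plan says.** SAP 2.1 gives this endpoint its own secondary objective: "To evaluate the time to treatment discontinuation/failure due to toxicity". SAP 3.2.1 lists it among the secondary safety endpoints. The clock starts at first dose. The event is stopping study treatment because of an adverse event ("discontinuation of either avelumab or axitinib for arm A") or death from treatment toxicity.

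The two documents then differ on the analysis:

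- Protocol 9.5: "Time to treatment discontinuation/failure due to toxicity will be summarized by treatment arm using Kaplan-Meier methodology", with a median and its 95% CI for each arm. It gives no censoring rule.
- SAP 6.6.5: time is the discontinuation date minus the start date plus one day, converted to months, and "TTF will be summarized using simple descriptive statistics (mean, SD, median, min, max, Q1, Q3"). It has no Kaplan-Meier estimate, confidence interval or censoring term.

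For duration of response, SAP 6.2.2.7 uses an event-or-censoring date and says that "DR will be displayed graphically and analyzed using Kaplan-Meier methodology". SAP 6.2.6.1 says that "Duration of ADA response will be displayed graphically and analyzed using Kaplan-Meier methodology", and gives that endpoint a censoring rule.

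SAP 6.6.6 separately reports the proportion stopping for toxicity, which "will be estimated by dividing the number of patients who meet the above criteria by the number of patients in the safety set", with an exact CI.

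**The concern.** Treatment also ends for progression, refusal, loss to follow-up or sponsor decision, and some patients are still on treatment at each of up to four cut-offs. SAP 6.6.5 does not say what happens to these patients. There are two readings:

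- **Event-only.** Only patients who stopped for toxicity contribute. This is the more natural reading. The summary is then conditional on toxicity arriving before any other stop and before the cut-off.
- **Everyone with a discontinuation date.** Stops for other causes are then counted as toxicity times.

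Either way the reported time reflects how long patients stay on treatment for other reasons and how late the data are cut. The arm with slower progression would tend to show later toxicity stops even with identical toxicity, and every later cut-off would lengthen the figure in both arms.

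Two dates are also unclear. The formula uses a discontinuation date, although toxic death is an event. In Arm A, SAP 3.4.1 dates the last dose of study treatment at the later of the two drugs, whereas the event is the stop of either one. The second of these needs only a clarification of wording.

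**Working it through.** The documents state no rate, power or sample size for this endpoint, so there is no planned figure to reproduce. The calculation shows how the SAP summary behaves when toxicity is set equal in the two arms.

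**Inputs**

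- Other-cause stopping: the planned PFS medians for unselected patients (SAP 5.1.1), 15.7 months (A) and 11 months (B). This is a loose proxy, because protocol 5.4.4 allows treatment past progression.
- Accrual over 21 months (SAP 5.1.1), taken as uniform; the SAP says non-uniform.
- Cut-offs at months 32 and 61 (SAP Tables 7 and 8, under the alternatives).
- Toxicity hazard h = 0.015 per month in both arms. This is an assumption; the documents give none.

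**Formulas**

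- Other-cause hazard o = ln2/median: 0.6931/15.7 = 0.0441 (A); 0.6931/11 = 0.0630 (B).
- Total hazard h + o: 0.0591 (A); 0.0780 (B).
- Follow-up is uniform between cut-off − 21 and cut-off; G(t) is the probability that it exceeds t.
- Event-only mean = ∫ t·h·exp(−(h+o)t)·G(t) dt ÷ ∫ h·exp(−(h+o)t)·G(t) dt.
- Proportion with the event = the denominator of that ratio.

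**What SAP 6.6.5 would report**

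| | Month 32, A v B | Month 61, A v B |
|---|---|---|
| Event-only mean (months) | 8.65 v 7.88 | 14.16 v 11.76 |
| Event-only median (months) | 7.3 v 6.5 | 10.8 v 8.6 |
| Patients with the event | 17.8% v 15.2% | 24.0% v 18.8% |
| Patients left out | 82% v 85% | 76% v 81% |

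A simulation of 2,000,000 patients per arm agrees: 8.64 v 7.89 and 14.17 v 11.74. Using all stoppers gives 8.65 v 7.87 and 14.15 v 11.76, so the choice of reading hardly matters here. With unlimited follow-up the event-only mean tends to 1/(h+o): 16.9 v 12.8 months.

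The summary also responds weakly to toxicity itself. Doubling h to 0.030 at month 32 raises the Arm A event share from 17.8% to 31.4%, yet the mean moves only from 8.65 to 8.03 months.

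**Range of the difference in means (A − B)**

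| Varied input | Month 32 | Month 61 |
|---|---|---|
| Arm A other-cause median 11, 13.35, 15.7, 20 months | 0, 0.4, 0.8, 1.2 | 0, 1.3, 2.4, 3.8 |
| h from 0.010 to 0.030, equal in both arms | 0.8 to 0.7 | 2.6 to 2.0 |

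**Alternatives in the same scenario**

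- Kaplan-Meier risk, 1 − exp(−ht), at 6, 12 and 24 months: 8.6%, 16.5%, 30.2% in both arms, at either cut-off for which the time is observed.
- Cumulative incidence, h/(h+o)·(1 − exp(−(h+o)t)): 7.6%, 12.9%, 19.2% (A) v 7.2%, 11.7%, 16.3% (B).
- Kaplan-Meier median, ln2/0.015 = 46 months: not reached at the month-32 cut-off. At month 61, with 830/2 = 415 per arm, the number at risk there is 415·exp(−(h+o)·46.2)·(61 − 46.2)/21, about 19 (A) and 8 (B). At 12 months it is 204 and 163.

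**If other-cause stopping is not independent of toxicity.** A gamma frailty shared by both hazards, with variance 0.5 or 1.0, gives a true 12-month risk of 1 − 1.09⁻² = 15.8% or 1 − 1/1.18 = 15.3% in both arms. Kaplan-Meier then gives 14.3% v 13.7%, or 12.7% v 11.9%.

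**The case against.** The strongest defence is that the event-only summary is a definable quantity. SAP 6.6.6 says how many patients stopped for toxicity, SAP 6.6.5 says when among those who did, and no comparison between arms is planned. That is fair as far as it goes, and it is why any descriptive summary that is kept should be labelled that way. But SAP 6.6.5 does not restrict the endpoint to patients with the event, and timing among events still moves with other-cause stopping and with the cut-off. The proportion in SAP 6.6.6 is valid but carries no timing and reflects unequal exposure. The exposure, disposition and adverse-event tables give context without repairing the figure.

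The SAP also uses plain descriptive statistics elsewhere. Time to ADA response is one case, and time to tumour response is another: "Time to response (TTR) is defined, for patients with OR, as the time from the date of randomization". Both are restricted by definition to patients who had the event, so they are not parallels. Time to deterioration, which is not restricted, uses Kaplan-Meier.

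Three points stand:

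- SAP section 2 allows changes to non-primary analyses, and the SAP's table of changes was not available here, so no procedural breach is claimed.
- The arm difference is modest at month 32.
- The alternatives have limits. Kaplan-Meier needs independent other-cause stopping, and cumulative incidence also varies with other-cause stopping, although it states that dependence openly and estimates a real-world risk.

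**Conclusion.** The concern holds. Followed as written, SAP 6.6.5 gives a time that does not describe toxicity alone. In the illustration, with equal toxicity, the means differ between arms by 0.8 months at month 32 and 2.4 months at month 61. Between those cut-offs the mean rises by 64% in Arm A (14.16/8.65) and 49% in Arm B (11.76/7.88).

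These sizes rest on assumed constant hazards, the PFS proxy and uniform accrual. The arm difference is zero if other-cause stopping is equal; the dependence on cut-off remains. Neither document supplies a complete analysis, since the protocol names the method without a censoring rule. No alpha, test or efficacy result is affected. It should be corrected because a stated secondary objective otherwise has no interpretable estimate of timing.

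**What to change.** Rewrite SAP 6.6.5 as follows:

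- **Event and date:** first stop of either drug for an adverse event (Arm A) or of sunitinib (Arm B), dated at that drug's stop; or toxic death, dated at death.
- **Censoring:** at the cut-off if still on treatment; at last dose if stopped for another reason. State that this assumes other-cause stopping is independent of toxicity.
- **Estimates by arm:** Kaplan-Meier curve, median with 95% CI where reached, and rates at fixed times such as 6, 12 and 24 months. The fixed times are needed because the median may not be reached or may rest on very few patients.
- **Companion estimate:** cumulative incidence with other-cause discontinuation as a competing event. This does not need the independence assumption; note that it reflects other-cause stopping as it occurred in each arm.
- **Label:** describe any retained mean, SD or quartiles as being among patients with the event only.

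The first three items restore the protocol's method and complete it; the fixed-time rates and cumulative incidence are additions to both documents. The cost is one paragraph of SAP text and one standard table and figure, with no new data.

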6.6.6. Treatment discontinuation due to toxicity

Treatment discontinuation due to toxicity is defined as the discontinuation of study treatment (discontinuation of either avelumab or axitinib for arm A) due to an adverse event or death due to study treatment toxicity. The number and percentage of patients who discontinue treatment due to toxicity in each treatment arm will be estimated by dividing the number of patients who meet the above criteria by the number of patients in the safety set.

The corresponding exact 2-sided 95% CIs will be provided for each treatment arm, using the Clopper-Pearson method (exact CI for a binomial proportion as computed by default by the FREQ procedure using the EXACT option).

6.6.7. Laboratory data

6.6.7.1. Hematology and chemistry parameters

Laboratory results will be classified according to the NCI-CTCAE criteria version 4.03. Non-numerical qualifiers (with the exception of fasting flags) will not be taken into consideration in the derivation of CTCAE criteria (e.g., hypokalemia Grade 1 and Grade 2 are only distinguished by a non-numerical qualifier and therefore Grade 2 will not be derived). Additional laboratory results that are not part of NCI-CTCAE will be presented according to the categories: below normal limit, within normal limits and above normal limit (according to the laboratory normal ranges).

Quantitative data will be summarized using simple descriptive statistics (mean, SD, median, Q1, Q3, minimum, and maximum) of actual values and changes from baseline for each nominal visit over time (unscheduled measurements would therefore not be included in these summaries as described in Section 5.2.9). End of Treatment visit laboratory results will be summarized separately. The changes computed will be the differences from baseline. Qualitative data based on reference ranges will be described according to the categories (i.e., Low, Normal, High).

Abnormalities classified according to NCI-CTCAE toxicity grading version 4.03 will be described using the worst grade. For those parameters which are graded with two toxicities such as potassium (hypokalemia/hyperkalemia), the toxicities will be summarized separately. Low direction toxicity (e.g., hypokalemia) grades at baseline and post baseline will be set to 0 when the variables are derived for summarizing high direction toxicity (e.g., hyperkalemia), and vice versa.

For **WBC differential counts** (total neutrophil [including bands], lymphocyte, monocyte, eosinophil, and basophil counts), the absolute value will be used when reported. When only percentages are available (this is mainly important for neutrophils and lymphocytes, because the CTCAE grading is based on the absolute counts), the absolute value is derived as follows:

$$\text{Derived differential absolute count} = (\text{WBC count}) \times (\text{Differential \%value} / 100)$$

If the range for the differential absolute count is not available (only range for value in % is available) then Grade 1 will be attributed to as follows:

- Lymphocyte count decreased:
 - derived absolute count does not meet Grade 2-4 criteria, and
 - % value < % LLN value, and
 - derived absolute count $\geq 800/\text{mm}^3$
- Neutrophil count decreased
 - derived absolute count does not meet Grade 2-4 criteria, and
 - % value < % LLN value, and

- derived absolute count $\geq 1500/\text{mm}^3$

For **calcium**, CTCAE grading is based on Corrected Calcium and Ionized Calcium (CALCIO). Corrected Calcium is calculated from Albumin and Calcium as follows:

Corrected calcium (mmol/L) = measured total Calcium (mmol/L) + 0.02 (40 - serum albumin [g/L])

Liver function tests: Alanine aminotransferase (ALT), aspartate aminotransferase (AST), and total bilirubin (TBILI) are used to assess possible drug induced liver toxicity. The ratios of test result over upper limit of normal (ULN) will be calculated and classified for these three parameters during the on-treatment period.

Summary of liver function tests will include the following categories. The number and percentage of patients with each of the following during the on-treatment period will be summarized by treatment arm:

- $\text{ALT} \geq 3 \times \text{ULN}$, $\text{ALT} \geq 5 \times \text{ULN}$, $\text{ALT} \geq 10 \times \text{ULN}$, $\text{ALT} \geq 20 \times \text{ULN}$
- $\text{AST} \geq 3 \times \text{ULN}$, $\text{AST} \geq 5 \times \text{ULN}$, $\text{AST} \geq 10 \times \text{ULN}$, $\text{AST} \geq 20 \times \text{ULN}$
- $(\text{ALT or AST}) \geq 3 \times \text{ULN}$, $(\text{ALT or AST}) \geq 5 \times \text{ULN}$, $(\text{ALT or AST}) \geq 10 \times \text{ULN}$, $(\text{ALT or AST}) \geq 20 \times \text{ULN}$
- $\text{TBILI} \geq 2 \times \text{ULN}$
- Concurrent $\text{ALT} \geq 3 \times \text{ULN}$ and $\text{TBILI} \geq 2 \times \text{ULN}$
- Concurrent $\text{AST} \geq 3 \times \text{ULN}$ and $\text{TBILI} \geq 2 \times \text{ULN}$
- Concurrent $(\text{ALT or AST}) \geq 3 \times \text{ULN}$ and $\text{TBILI} \geq 2 \times \text{ULN}$
- Concurrent $(\text{ALT or AST}) \geq 3 \times \text{ULN}$ and $\text{TBILI} \geq 2 \times \text{ULN}$ and $\text{ALP} > 2 \times \text{ULN}$
- Concurrent $(\text{ALT or AST}) \geq 3 \times \text{ULN}$ and $\text{TBILI} \geq 2 \times \text{ULN}$ and $(\text{ALP} \leq 2 \times \text{ULN}$ or missing).

Concurrent measurements are those occurring on the same date.

Categories will be cumulative, i.e., a patient with an elevation of $\text{AST} \geq 10 \times \text{ULN}$ will also appear in the categories $\geq 5 \times \text{ULN}$ and $\geq 3 \times \text{ULN}$. Liver function elevation and possible Hy's Law cases will be summarized using frequency counts and percentages.

An evaluation of Drug-Induced Serious Hepatotoxicity (eDISH) plot will also be created, with different symbols for different treatment arms, by graphically displaying

- peak serum ALT(/ULN) vs peak total bilirubin (/ULN) including reference lines at $\text{ALT}=3 \times \text{ULN}$ and $\text{total bilirubin}=2 \times \text{ULN}$.
- peak serum AST(/ULN) vs peak total bilirubin (/ULN) including reference lines at $\text{AST}=3 \times \text{ULN}$ and $\text{total bilirubin}=2 \times \text{ULN}$.

In addition, a listing of all TBILI, ALT, AST and ALP values for patients with a post-baseline TBILI $\geq 2 \times \text{ULN}$, ALT $\geq 3 \times \text{ULN}$ or AST $\geq 3 \times \text{ULN}$ will be provided.

Parameters with NCI-CTC grades available:

The laboratory toxicities will be tabulated using descriptive statistics (number of patients and percentages) during the on-treatment period. The denominator to calculate percentages for each laboratory parameter is the number of patients evaluable for CTCAE grading (i.e. those patients for whom a Grade 0, 1, 2, 3 or 4 can be derived).

- The summary of laboratory parameters by CTCAE grade table will include number and percentage of patients with Grade 1, 2, 3, 4, Grade 3/4 and any grade (Grades 1-4), laboratory abnormalities during the on-treatment period.
- The shift table will summarize baseline CTCAE grade versus the worst on-treatment CTCAE grade. The highest CTCAE grade during the on-treatment period is considered as the worst grade for the summary.

The above analyses apply to hematology and chemistry evaluations which can be graded per CTCAE, i.e.:

- Hematology:

Hemoglobin (HB), Leukocytes (white blood cell decreased), Lymphocytes (lymphocyte count increased/decreased), Neutrophils / Absolute Neutrophils Count (ANC) (neutrophil count decreased), Platelet Count (PLT) (platelet count decreased).

- Serum Chemistry:

Albumin (hypoalbuminemia), Alkaline Phosphatase (alkaline phosphatase increased), Alanine Aminotransferase (ALT) (ALT increased), Amylase (serum amylase increased), Aspartate Aminotransferase (AST) (AST increased), Total Bilirubin (blood bilirubin increased), Cholesterol (cholesterol high), Creatinine (creatinine increased), Creatine Kinase (CPK increased), Potassium (hypokalemia/ hyperkalemia), Sodium (hyponatremia/ hypernatremia), Magnesium (hypomagnesemia/hypermagnesemia), Calcium (hypocalcemia/ hypercalcemia), Glucose (hypoglycemia/hyperglycemia), Gamma Glutamyl Transferase (GGT) (GGT increased), Lipase (lipase increased), Phosphates (hypophosphatemia), Triglycerides (hypertriglyceridemia).

Parameters with NCI-CTC grades not available:

Hematology and chemistry evaluations which cannot be graded per CTCAE criteria will be summarized as frequency (number and percentage) of patients with:

- shifts from baseline normal to at least one result above normal during on-treatment period
- shifts from baseline normal to at least one result below normal during on-treatment period

In this study, these apply to the following parameters:

- Hematology: Absolute Monocytes, Absolute Eosinophils, Absolute Basophils
- Serum Chemistry: Chloride, Total Urea, Uric Acid, Total Protein, C-Reactive Protein, Lactate Dehydrogenase (LDH), B-type natriuretic peptide (BNP), troponin, and CK-MB

